- If the toxicities do resolve and conditions are aligned with what is defined in Table 3, the combination of lenvatinib and pembrolizumab may be restarted at the discretion of the investigator. In these cases where the toxicity is attributed to the combination or to lenvatinib alone, re-initiation of pembrolizumab as a monotherapy may be considered at the principal investigator's discretion .]

Table 3. Dose modification and toxicity management guidelines for immune-related AEs associated with pembrolizumab monotherapy and IO Combinations

General instructions:				

 1. Severe and life-threatening irAEs should be treated with IV corticosteroids followed by oral steroids. Other immunosuppressive treatment should begin if the irAEs are not controlled by corticosteroids. 2. Study intervention must be permanently discontinued if the irAE does not resolve or the corticosteroid dose is not ≤ 10 mg/day within 12 weeks of the last study intervention treatment. 3. The corticosteroid taper should begin when the irAE is \leq Grade 1 and continue at least 4 weeks. 4. If study intervention has been withheld, study intervention may resume after the irAE decreased to \leq Grade 1 after corticosteroid taper. 				

irAEs	Toxicity Grade (CTCAE v5.0)	Action With Pembrolizumab	Corticosteroid and/or Other Therapies	Monitoring and Follow-up
Pneumonitis	Grade 2	Withhold	
 • Administer corticosteroids (initial dose of 1 to 2 mg/kg prednisone or equivalent) followed by taper • Add prophylactic antibiotics for opportunistic infections 	
 • Monitor participants for signs and symptoms of pneumonitis • Evaluate participants with suspected pneumonitis with radiographic imaging and initiate corticosteroid treatment
	Recurrent Grade 2, Grade 3 or 4	Permanently discontinue		
Diarrhea/Colitis	Grade 2 or 3	Withhold	
 • Administer corticosteroids (initial dose of 1 to 2 mg/kg prednisone or equivalent) followed by taper 	
 • Monitor participants for signs and symptoms of enterocolitis (ie, diarrhea, abdominal pain, blood or mucus in stool with or without fever) and of bowel perforation (ie, peritoneal signs and ileus)

irAEs	Toxicity Grade (CTCAE v5.0)	Action With Pembrolizumab	Corticosteroid and/or Other Therapies	Monitoring and Follow-up

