	Recurrent Grade 3 or Grade 4	Permanently discontinue		
 Participants with \geqGrade 2 diarrhea suspecting colitis should consider GI consultation and performing endoscopy to rule out colitis Participants with diarrhea/colitis should be advised to drink liberal quantities of clear fluids. If sufficient oral fluid intake is not feasible, fluid and electrolytes should be substituted via IV infusion
AST or ALT Elevation or Increased Bilirubin	Grade 2 ^a	Withhold	
 Administer corticosteroids (initial dose of 0.5 to 1 mg/kg prednisone or equivalent) followed by taper 	
 Monitor with liver function tests (consider weekly or more frequently until liver enzyme value returned to baseline or is stable)
	Grade 3 ^b	Withhold; discontinue only if not improving on steroids within 7 days	
 Administer corticosteroids (initial dose of 1 to 2 mg/kg prednisone or equivalent) followed by taper 	
	Grade 4 ^c	Permanently discontinue	Administer corticosteroids (initial dose of 1 to 2 mg/kg prednisone or equivalent) followed by taper	
T1DM or Hyperglycemia	New onset T1DM or Grade 3 or 4 hyperglycemia	Withhold ^d	
 Initiate insulin replacement therapy for participants with T1DM 	
 Monitor participants for hyperglycemia or other signs and symptoms of diabetes

irAEs	Toxicity Grade (CTCAE v5.0)	Action With Pembrolizumab	Corticosteroid and/or Other Therapies	Monitoring and Follow-up
	associated with evidence of β -cell failure		
 Administer antihyperglycemic in participants with hyperglycemia 	
Hypophysitis	Grade 2-3	Continue unless clinically unstable	
 Administer corticosteroids and initiate hormonal replacements as clinically indicated 	
 Monitor for signs and symptoms of hypophysitis (including hypopituitarism and adrenal insufficiency)
	Grade 4	Withhold	
 The decision to withhold or permanently discontinue pembrolizumab is at the discretion of the investigator or treating physician. If control achieved or \leq Grade 2, pembrolizumab may be resumed. 	

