Hyperthyroidism	Grade 2	Continue	
 Treat with nonselective beta-blockers (eg, propranolol) or thionamides as appropriate 	
 Monitor for signs and symptoms of thyroid disorders
	Grade 3 or 4	Withhold	
 The decision to withhold or permanently discontinue pembrolizumab is at the discretion of the investigator or treating physician. If control achieved or \leq Grade 2, pembrolizumab may be resumed. 	

irAEs	Toxicity Grade (CTCAE v5.0)	Action With Pembrolizumab	Corticosteroid and/or Other Therapies	Monitoring and Follow-up
Hypothyroidism	Grade 2, 3 or 4	Continue	
 Initiate thyroid replacement hormones (eg, levothyroxine or liothyronine) per standard of care 	
 Monitor for signs and symptoms of thyroid disorders
Nephritis: grading according to increased creatinine or acute kidney injury	Grade 2-3	Withhold	
 Administer corticosteroids (prednisone 1 to 2 mg/kg or equivalent) followed by taper 	
 Monitor changes of renal function
	Grade 4	Permanently discontinue		
Neurological Toxicities	Grade 2	Withhold	
 Based on severity of AE administer corticosteroids 	
 Ensure adequate evaluation to confirm etiology and/or exclude other causes
	Grade 3 or 4	Permanently discontinue		
Myocarditis	Grade 2	Withhold	
 Based on severity of AE administer corticosteroids 	
 Ensure adequate evaluation to confirm etiology and/or exclude other causes
	Grade 3 or 4	Permanently discontinue		
Exfoliative Dermatologic Conditions	Suspected SJS, TEN, or DRESS	Withhold	
 Based on severity of AE administer corticosteroids 	
 Ensure adequate evaluation to confirm etiology or exclude other causes
	Confirmed SJS, TEN, or DRESS	Permanently discontinue		
All Other irAEs	Persistent Grade 2	Withhold	
 Based on severity of AE administer corticosteroids 	
 Ensure adequate evaluation to confirm etiology or exclude other causes
	Grade 3	Withhold or discontinue based on the event ^d		

irAEs	Toxicity Grade (CTCAE v5.0)	Action With Pembrolizumab	Corticosteroid and/or Other Therapies	Monitoring and Follow-up

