	Recurrent Grade 3 or Grade 4	Permanently discontinue		

AE(s)=adverse event(s); ALT= alanine aminotransferase; AST=aspartate aminotransferase; CTCAE=Common Terminology Criteria for Adverse Events; DRESS=Drug Rash with Eosinophilia and Systemic Symptom; GI=gastrointestinal; IO=immuno-oncology; ir=immune related; IV=intravenous; SJS=Stevens-Johnson Syndrome; T1DM=type 1 diabetes mellitus; TEN=Toxic Epidermal Necrolysis; ULN=upper limit of normal.
 
Note: Non-irAE will be managed as appropriate, following clinical practice recommendations.
 
^a AST/ALT: >3.0 to 5.0 x ULN if baseline normal; >3.0 to 5.0 x baseline, if baseline abnormal; bilirubin:>1.5 to 3.0 x ULN if baseline normal; >1.5 to 3.0 x baseline if baseline abnormal
 
^b AST/ALT: >5.0 to 20.0 x ULN, if baseline normal; >5.0 to 20.0 x baseline, if baseline abnormal; bilirubin:>3.0 to 10.0 x ULN if baseline normal; >3.0 to 10.0 x baseline if baseline abnormal
 
^c AST/ALT: >20.0 x ULN, if baseline normal; >20.0 x baseline, if baseline abnormal; bilirubin: >10.0 x ULN if baseline normal; >10.0 x baseline if baseline abnormal
 
^d The decision to withhold or permanently discontinue pembrolizumab is at the discretion of the investigator or treating physician. If control achieved or ≤ Grade 2, pembrolizumab may be resumed.
 
^e Events that require discontinuation include, but are not limited to: encephalitis and other clinically important irAEs (eg, vasculitis and sclerosing cholangitis).
				

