5.6 Participant Withdrawal/Discontinuation Criteria

Discontinuation of study intervention does not represent withdrawal from the study.

As certain data on clinical events beyond study intervention discontinuation may be important to the study, they must be collected through the participant's last scheduled follow-up, even if the participant has discontinued study intervention. Therefore, all participants who discontinue study intervention prior to completion of the protocol-specified treatment period will still continue to participate in the study as specified in Section 7.1.4.

Participants may discontinue study intervention at any time for any reason or be discontinued from the study intervention at the discretion of the investigator should any untoward effect occur. In addition, a participant may be discontinued from study intervention by the investigator or the study PI if study intervention is inappropriate, the study plan is violated, or for administrative and/or other safety reasons. Specific details regarding procedures to be performed at study intervention discontinuation are provided in Section 7.1.5.3.

A participant must be discontinued from study treatment but continue to be monitored in the study for any of the following reasons:

- The participant or participant's legally acceptable representative requests to discontinue study treatment.
- Confirmed radiographic disease progression outlined in Section 7.1.2.9. Patients who are believed to be deriving benefit based on the discretion of the investigator and PI are allowed to continue.
- Any progression or recurrence of any malignancy, or any occurrence of secondary malignancy that requires active treatment. Exceptions to secondary malignancy include basal cell carcinoma of the skin, squamous cell carcinoma of the skin, new non-ulcerated primary melanoma <1 mm in depth with no nodal involvement, or carcinoma in situ (eg, breast carcinoma, cervical cancer in situ) that have undergone potentially curative therapy. Exceptions should be discussed with the study PI prior to continuing therapy or remaining in follow-up.
- Unacceptable adverse experiences as described in Section 5.2.2.

- The participant has a medical condition or personal circumstance which, in the opinion of the investigator and/or sponsor, placed the participant at unnecessary risk from continued administration of study treatment.
- The participant has a confirmed positive serum pregnancy test.

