	Time Course	
Did the AE follow in a reasonable temporal sequence from administration of Merck product?
 
Is the time of onset of the AE compatible with a drug-induced effect (applies to trials with investigational medicinal product)?

	Likely Cause	Is the AE not reasonably explained by another etiology such as underlying disease, other drug(s)/vaccine(s), or other host or environmental factors

Relationship	The following components are to be used to assess the relationship between the test drug and the AE: (continued)	
to Merck Product (continued)	Dechallenge	
Was Merck product discontinued or dose/exposure/frequency reduced?
 
If yes, did the AE resolve or improve?
 
If yes, this is a positive dechallenge. If no, this is a negative dechallenge.
 
(Note: This criterion is not applicable if: (1) the AE resulted in death or permanent disability; (2) the AE resolved/improved despite continuation of the Sponsor's product; or (3) the trial is a single-dose drug trial); or (4) Sponsor's product(s) is/are only used one time.)

	Rechallenge	
Was the participant re-exposed to Merck product in this study?
 
If yes, did the AE recur or worsen?
 
If yes, this is a positive rechallenge. If no, this is a negative rechallenge.
 
(Note: This criterion is not applicable if: (1) the initial AE resulted in death or permanent disability, or (2) the trial is a single-dose drug trial); or (3) Sponsor's product(s) is/are used only one time).
 
NOTE: IF A RECHALLENGE IS PLANNED FOR AN ADVERSE EVENT WHICH WAS SERIOUS AND WHICH MAY HAVE BEEN CAUSED BY MERCK PRODUCT, OR IF REEXPOSURE TO MERCK PRODUCT POSES ADDITIONAL POTENTIAL SIGNIFICANT RISK TO THE PARTICIPANT, THEN THE RECHALLENGE MUST BE APPROVED IN ADVANCE BY THE SPONSOR AS PER DOSE MODIFICATION GUIDELINES IN THE PROTOCOL.

	Consistency with Trial Treatment Profile	Is the clinical/pathological presentation of the AE consistent with previous knowledge regarding Merck product or drug class pharmacology or toxicology?
The assessment of relationship will be reported on the case report forms /worksheets by an investigator who is a qualified physician according to his/her best clinical judgment, including consideration of the above elements.		
Record one of the following	Use the following scale of criteria as guidance (not all criteria must be present to be indicative of Merck product relationship).	

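### Table 3 marks the Grade 3 row for all other immune-related events with footnote d (discretion, may resume), and no cell calls footnote e, the list of mandatory stops

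*Combined protocol and SAP*

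**What the plan says.** Table 3 (section 5.2.2.1) sets what is done with study treatment for each irAE and grade. Its last row covers all irAEs not named elsewhere. For Grade 3 in that row the action is "Withhold or discontinue based on the event", followed by superscript d.

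The two footnotes at issue are printed one after the other under the table:

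- Footnote d: "The decision to withhold or permanently discontinue pembrolizumab is at the discretion of the investigator or treating physician". It continues: "If control achieved or ≤ Grade 2, pembrolizumab may be resumed".
- Footnote e: "Events that require discontinuation include, but are not limited to: encephalitis and other clinically important irAEs (eg, vasculitis and sclerosing cholangitis".

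The only other cell with superscript d is the withhold action for "New onset T1DM or Grade 3 or 4 hyperglycemia" with evidence of beta-cell failure. The table's general instruction 4 gives the default restart rule: "If study intervention has been withheld, study intervention may resume after the irAE decreased to" Grade 1 or lower, after the corticosteroid taper.

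**The concern.** Footnote e is the only place in the table that names particular events for which treatment must stop, and nothing points to it. The cell it appears to belong to points to footnote d, which says close to the opposite: the physician decides, and dosing may restart once the event is controlled or is at Grade 2 or lower.

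Table 3 is an operative rule. Section 5.2.2.1 requires both drugs to be held by its criteria and allows the combination to be restarted when the conditions in the table are met. A site that looks up a first Grade 3 vasculitis or sclerosing cholangitis and follows the superscript is sent to discretionary restart. At stake is the safety of the individual patient; the efficacy analysis is not touched.

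**Working it through.** The plan states no figure to reproduce here. The check is a trace of every superscript in Table 3 to its footnote, followed by a reading of the content.

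**1. Callouts in reading order**

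| Cell | Marker |
|---|---|
| AST/ALT/bilirubin, Grade 2 | a |
| AST/ALT/bilirubin, Grade 3 | b |
| AST/ALT/bilirubin, Grade 4 | c |
| Type 1 diabetes or hyperglycemia | d |
| All other irAEs, Grade 3 | d |

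Count by footnote: a 1, b 1, c 1, d 2, e 0. That is 1 + 1 + 1 + 2 + 0 = 5 callouts for five footnotes. The fifth callout, where e is due, is the cell in question.

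**2. Which footnote fits the cell**

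The cell makes the action depend on which event has occurred. Footnote e lists events; footnote d lists none. Footnote d's two sentences also appear in full in the Grade 4 hypophysitis and Grade 3 or 4 hyperthyroidism rows, and d is called by the diabetes row. All three are endocrine. Rows under the Grade 2 restart wording:

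- marker d on this cell: 3 endocrine + 1 = 4 rows;
- marker e on this cell: 3 rows, all endocrine.

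**3. What the marker changes for a first Grade 3 event in this row**

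| | Marker d | Marker e |
|---|---|---|
| Vasculitis, sclerosing cholangitis | Physician's choice; may restart if controlled or at Grade 2 or lower | Must stop |
| Events that footnote e does not cover | Same as above | Withhold or stop; restart under general instruction 4, at Grade 1 or lower after taper |

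**4. What the marker does not change**

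- Recurrent Grade 3 and Grade 4 events in this row are permanent stops.
- Grade 3 or 4 neurological toxicities have their own row and are permanent stops, which would ordinarily cover Grade 3 encephalitis.
- General instruction 2 stops treatment permanently if the irAE has not resolved, or steroids are not down to 10 mg/day, within 12 weeks.
- The rechallenge note in Table 7 (section 7.2.4) covers an event that was serious and possibly drug-related, or re-exposure that carries additional significant risk: "THEN THE RECHALLENGE MUST BE APPROVED IN ADVANCE BY THE SPONSOR AS PER DOSE MODIFICATION GUIDELINES IN THE PROTOCOL".
- Section 5.6 requires stopping where a medical condition or circumstance, in the opinion of the investigator and/or sponsor, "placed the participant at unnecessary risk from continued administration of study treatment".

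What remains exposed is a first, non-neurological Grade 3 event that footnote e would stop.

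**5. Could the letter be a reading error?**

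The text was taken from PDF and the row crosses a page break, so e could have been read as d. The same extraction does keep d and e apart in Table 3's own footnote labels and in Table 5 (section 5.2.2.5), where markers a to e are each called once. That makes a misread less likely but does not rule it out.

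**The case against.** The strongest reply is that this may not be an error in the plan at all. The case rests on one superscript in a machine-read table. The pattern used as evidence, five callouts in order with an event-dependent action in the fifth, is what a correct table with e misread as d would also look like. Table 5 is a thin control, with one d and one e, and footnote labels in alphabetical order are easier to read than a lone superscript. This stands as a limit on confidence, and it is why the remedy starts with a look at the source file.

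The second reply is that little harm follows even if d is really there. Footnote e is printed directly below d in mandatory terms, and a reader may well take the specific list to override general discretion. Footnote d itself permits stopping. Grade 3 events often lead to hospitalization, which makes them serious, so the sponsor-approval requirement in Table 7 would often apply to a restart. Much of this stands, and it keeps the point small. It does not remove it. An uncalled footnote is tied to no row or grade, and the footnote the cell does call says that dosing may resume. The Table 7 note refers the reader back to the dose modification guidelines, and so to this table. The section 5.6 criterion is a judgement and names no events. These checks reduce the chance of a wrong restart; none corrects the marker.

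**Conclusion.** The concern holds for the table as supplied. The Grade 3 cell for all other irAEs calls footnote d, and footnote e is called by no cell. Read literally, this permits restart after first Grade 3 events that footnote e says must end treatment, and at a looser grade than general instruction 4.

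It is a minor point: one cell of one table, limited to first Grade 3 events in that row that footnote e would stop. The documents give no rate for such events, so no number of patients is claimed. Endpoint, sample size, alpha and power are unaffected. Confidence is medium, because the conclusion assumes that the superscript was read correctly from the PDF.

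**What to change.** Check the superscript on the Grade 3 action for all other irAEs against the protocol's source file. If it is d, change it to e. The events covered by footnote e then become mandatory stops, and other Grade 3 events in the row restart under general instruction 4. If the source already shows e, nothing needs to change.

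The cost is at most one character in Table 3, with no added procedures or visits.

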5.2.2.2 Dose modification and toxicity management of infusion-reactions related to pembrolizumab

Pembrolizumab may cause severe or life-threatening infusion-reactions including severe hypersensitivity or anaphylaxis. Signs and symptoms usually develop during or shortly after drug infusion and generally resolve completely within 24 hours of completion of infusion. Dose modification and toxicity management guidelines on pembrolizumab associated infusion reaction are provided in Table 4.

NCI CTCAE Grade	Treatment	Premedication at Subsequent Dosing
Grade 1 Mild reaction; infusion interruption not indicated; intervention not indicated	Increase monitoring of vital signs as medically indicated until the participant is deemed medically stable in the opinion of the investigator.	None
Grade 2 Requires therapy or infusion interruption but responds promptly to symptomatic treatment (e.g., antihistamines, NSAIDs, narcotics, IV fluids); prophylactic medications indicated for ≤ 24 hrs	
Stop Infusion.
 
Additional appropriate medical therapy may include but is not limited to:
 
IV fluids
 
Antihistamines
 
NSAIDs
 
Acetaminophen
 
Narcotics
 
Increase monitoring of vital signs as medically indicated until the participant is deemed medically stable in the opinion of the investigator.
 
If symptoms resolve within 1 hour of stopping drug infusion, the infusion may be restarted at 50% of the original infusion rate (e.g. from 100 mL/hr to 50 mL/hr).
 
Otherwise dosing will be held until symptoms resolve and the participant should be premedicated for the next scheduled dose.
	Participant may be premedicated 1.5h (\pm 30 minutes) prior to infusion of pembrolizumab with: Diphenhydramine 50 mg po (or equivalent dose of antihistamine). Acetaminophen 500-1000 mg po (or equivalent dose of analgesic).

Grades 3 or 4
 
Grade 3: Prolonged (i.e., not rapidly responsive to symptomatic medication and/or brief interruption of infusion); recurrence of symptoms following initial improvement; hospitalization indicated for other clinical sequelae (e.g., renal impairment, pulmonary infiltrates)
 
Grade 4: Life-threatening; pressor or ventilatory support indicated
	
Stop Infusion.
 
Additional appropriate medical therapy may include but is not limited to:
 
Epinephrine**
 
IV fluids
 
Antihistamines
 
NSAIDs
 
Acetaminophen
 
Narcotics
 
Oxygen
 
Pressors
 
Corticosteroids
 
Increase monitoring of vital signs as medically indicated until the participant is deemed medically stable in the opinion of the investigator.
 
Hospitalization may be indicated.
 
**In cases of anaphylaxis, epinephrine should be used immediately.
 
For Grade 4 reaction, participant is permanently discontinued from further study drug treatment.
	No subsequent dosing

Appropriate resuscitation equipment should be available at the bedside and a physician readily available during the period of drug administration.
 
For further information, please refer to the Common Terminology Criteria for Adverse Events v5.0 (CTCAE) at http://ctep.cancer.gov
		

5.2.2.3 Other allowed dose interruption for pembrolizumab

Pembrolizumab may be interrupted for situations other than treatment-related AEs such as medical / surgical events or logistical reasons not related to study therapy. Participants should be placed back on study therapy within 3 weeks of the scheduled interruption, unless otherwise discussed with the PI. The reason for interruption should be documented in the patient's study record.

5.2.2.4 Management of AEs associated with lenvatinib

Lenvatinib dose reduction and interruption for participants who experience lenvatinib- related toxicity that are not considered irAEs will be in accordance with the dose modification guidelines described in Table 5. An interruption of study treatment for more than 28 days will require PI consultation and approval before treatment can be resumed.

Adverse events will be graded using NCI CTCAE v5.0. For presumed non irAEs, investigators will decide the probability of the event being related to lenvatinib and whether dose modification or interruption/discontinuation, as applicable, of one or both drugs is required. The starting dose of lenvatinib is 20 mg/day for participants enrolled. Dose reductions of lenvatinib occur in succession based on the previous dose level (14, 10, and 8 mg/day). Any dose reduction below 8 mg/day must be discussed with the PI. Once the study drug dose has been reduced, it may not be increased at a later date, unless the dose was mistakenly decreased; in this situation, PI's approval is required to increase the dose.

Refer to the subsections below for management of hypertension (Section 5.2.2.6), proteinuria (Section 5.2.2.7), diarrhea (Section 5.2.2.8), hepatotoxicity (Section 5.2.2.9), thromboembolic events (Section 5.2.2.10), posterior reversible encephalopathy syndrome/reversible posterior leukoencephalopathy syndrome (PRES/RPLS; Section 5.2.2.11), hypocalcemia (Section 5.2.2.12), and hemorrhage (Section 5.2.2.13), as appropriate, before consulting the dose modification table (Table 5).

- BP should be well-controlled prior to the start of lenvatinib. Blood pressure should be monitored after 1 week of treatment with lenvatinib, then every 2 weeks for the first 2 months and at the beginning of each cycle thereafter while on treatment. If a patient develops systolic BP ≥ 150 mmHg or diastolic BP ≥ 90 mmHg active management is indicated.
- Urine protein should be monitored regularly. If urine dipstick $\geq 2+$ is detected, dose interruptions, adjustments, or discontinuation may be necessary. Discontinue in the event of nephrotic syndrome.
- Monitor and correct all electrolyte abnormalities in all patients.
- Liver function tests should be monitored before initiation of treatment, then every 2 weeks for the first 2 months and monthly thereafter during treatment. In the case of hepatotoxicity, dose interruptions, adjustments, or discontinuation may be necessary.

- Thyroid function, T3, T4 and TSH should be monitored before initiation of, and periodically throughout treatment with lenvatinib. Hypothyroidism should be treated according to standard medical practice to maintain euthyroid state.
- Monitor patients for clinical symptoms or signs of cardiac dysfunction as dose interruptions, adjustments, or discontinuation may be necessary.
- Gastrointestinal toxicity should be actively managed in order to reduce the risk of development of renal impairment or renal failure. Dose interruptions, adjustments, or discontinuation may be necessary.

5.2.2.5 Dose Reductions/ Interruptions for non-immune related Adverse Events attributed to Lenvatinib

Table 5 Dose Modification Guidelines for Lenvatinib-related Adverse Events

Treatment-Related Toxicity ^{a,b}	Management	Dose Adjustment
Grade 1 or Tolerable Grade 2	Continue treatment	No change
Intolerable Grade 2 ^c or Grade 3 ^d		
First occurrence	Interrupt lenvatinib until resolved to Grade 0-1, or tolerable Grade 2	Reduce lenvatinib dose to 14 mg once a day (1-level reduction)
Second occurrence (same toxicity or new toxicity)	Interrupt lenvatinib until resolved to Grade 0-1, or tolerable Grade 2	Reduce lenvatinib dose to 10 mg once a day (1-level reduction)
Third occurrence (same toxicity or new toxicity)	Interrupt lenvatinib until resolved to Grade 0-1, or tolerable Grade 2	Reduce lenvatinib dose to 8 mg orally once a day (1-level reduction)
Fourth occurrence (same toxicity or new toxicity)	Interrupt lenvatinib	Discuss with PI
Grade 4 ^e : Discontinue Study Treatment		

Note: For grading see CTCAE version 5.0. Collect all AE grades (ie, decreasing and increasing CTCAE grade).

a An interruption of study treatment for more than 28 days will require Sponsor's approval before treatment can be resumed.

b Initiate optimal medical management for nausea, vomiting, hypertension, hypothyroidism and/or diarrhea prior to any lenvatinib interruption or dose reduction.

c Applicable only to Grade 2 toxicities judged by the participant and/or physician to be intolerable.

d For asymptomatic laboratory abnormalities, such as Grade ≥ 3 elevations of amylase and lipase that are not considered clinically relevant by the investigator, continuation of treatment should be discussed with PI.

e Excluding laboratory abnormalities judged to be non-life-threatening, in which case manage as Grade 3.

Abbreviations: AE = adverse event; CTCAE = Common Terminology Criteria for Adverse Events

Other allowed dose interruptions for lenvatinib

Lenvatinib may be interrupted for situations other than treatment-related AEs such as medical / surgical events or logistical reasons not related to study therapy. Participants should be placed back on study therapy within 3 weeks of the scheduled interruption, unless otherwise discussed with the Sponsor. The reason for interruption should be documented in the patient's study record.

Indications for discontinuation of lenvatinib

Treatment should be discontinued in case of life-threatening reactions (e.g., Grade 4) with the exception of laboratory abnormality judged to be non-life-threatening, in which case they should be managed as severe reactions (e.g., Grade 3).

